6.6 TRANSFUSIONS

During the study period, packed RBC transfusion should be administered when hemoglobin <7g/dL, or <9g/dL with symptoms; platelet transfusion should be administered when platelet count <10g/dL. Additional transfusions may be administer per the discretion of the PI or the local HCT provider. The number of units transfused should be documented.

Transfusions between scheduled study visits can be done locally or at the sites per institutional standards.

7 STUDY INTERVENTION DISCONTINUATION AND PARTICIPANT DISCONTINUATION/WITHDRAWAL

7.1 DISCONTINUATION OF STUDY INTERVENTION

See section 6.1.2.3 for information on dosing modifications or discontinuation rules based on laboratory abnormalities or other adverse events.

Abbreviated Title: Fostamatinib for post-transplant cytopenias

Version Date: 11/28/2023

Subjects who have the study product stopped for safety related issues will not continue with dosing. In addition, subjects who have an allergic reaction that is temporally associated with study product administration and the PI believes it to be related to study product will not receive any more study product.

In addition, a subject in this clinical study may discontinue study drug at their request for any reason. Every effort should be made to encourage subjects to remain in the study for the duration of their planned outcome assessments. Subjects should be educated on the continued scientific importance of their data, even if they discontinue study drug.

Discontinuation from the study drug does not mean discontinuation from the study, and remaining study procedures should be completed as indicated by the study protocol. If a clinically significant finding is identified (including, but not limited to changes from baseline) after enrollment, the investigator or qualified designee will determine if any change in participant management is needed. Any new clinically relevant finding will be recorded as an adverse event (AE).

The data to be collected at the time of study intervention discontinuation will include the following:

- Reason for discontinuation
- Any adverse event
- Patients will be followed for clinical data required for the duration of the study

Participants are free to withdraw from participation in the study at any time upon request.

An investigator may discontinue or withdraw a participant from the study for the following reasons:

- Disease progression which requires discontinuation of the study intervention
- If any clinical adverse event (AE), laboratory abnormality, or other medical condition or situation occurs such that continued participation in the study would not be in the best interest of the participant
- Investigator discretion
- Positive pregnancy test
- Participant unable to receive study drug
- Participant non-compliance, defined as missing >20% of the study drug during any 4-week study interval
- If participant has drug interruptions more than 14 days due to toxicity (as defined at 6.1.2.3), participants will be withdrawn from the study.

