Elevated unconjugated (indirect) BL in absence of other LFT abnormalities	Continue fostamatinib with frequent monitoring since isolated increase in unconjugated (indirect) bilirubin may be due to UGT1A1 inhibition or active hemolysis
Diarrhea	
Diarrhea	
 • Manage diarrhea using supportive measures (e.g., dietary changes, hydration and/or antidiarrheal medication) early after the onset until symptom(s) have resolved. • If symptom(s) become severe (Grade 3 or above), temporarily interrupt fostamatinib. • If diarrhea improves to mild (Grade 1), resume fostamatinib at the next lower daily dose (refer to DSR).
Neutropenia	
Neutropenia	
 • If absolute neutrophil count decreases (ANC less than $1.0 \times 10^9/L$) and remains low after 72 hours, or the neutropenia can be attributed to other causes (see below), patient can receive standard dose (5mcg/kg or rounded to the closest vial or syringe size) filgrastim at the discretion of the primary team and continue fostamatinib. If neutropenia responds to filgrastim (ANC greater than $1.5 \times 10^9/L$), patient should continue fostamatinib. • If no other causes are identified and the neutropenia is attributed to fostamatinib, or patient does not respond to, or cannot receive filgrastim, temporarily interrupt fostamatinib until neutropenia resolves (ANC greater than $1.5 \times 10^9/L$), and resume fostamatinib at the next lower daily dose (refer to DSR).
Febrile neutropenia	Febrile neutropenia is a life-threatening complication and urgent broad-spectrum

	
antibiotics, as well as an aggressive search for the source and microbial cause of the episode.
 
 • First febrile neutropenia: hold fostamatinib then restart at the next lower dose level after resolution of febrile neutropenia (refer to DSR) • Second febrile neutropenia on the next lower dose level: stop fostamatinib and remove the patient from study
--	--

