- In the event that the subject is unable to tolerate 100 mg BID, the dose can be reduced to 150mg daily with re-assessment. If intolerable AEs with 150 mg daily, dose can be reduced to 100 mg daily. If unable to tolerate 100mg daily, patient will stop fostamatinib and will be off study. Intolerance is considered as any grade 3-4 AEs, probably or definitely related to fostamatinib, or any grade AE which, at the PI's discretion, appears to be distressing enough to the patient to lead to the drug's discontinuation. If the adverse events resolved and subject tolerates the dose reduction with no recurrence of AE, per PI discretion subject can be re-escalated one level at a time until back to the maximum tolerable dose.
- Causes of neutropenia in a AHCT recipient may include: infections such as cytomegalovirus infection, medication such as ganciclovir or other antibiotics, immunosuppressants such as mycophenolate or ruxolitinib, graft failure, relapse of primary disease. If neutropenia occurs, we will perform an extensively work up on the patient for the other causes stated above, and/or hold other potential culprit medications. We will give filgrastim to patients while doing the above work up. If no other causes are found, and the neutropenia does not recover, or recurs, with holding other medications, we will conclude that fostamatinib is contributing to the development of neutropenia.
- GvHD may mimic adverse events. If holding fostamatinib according to the DSR does not reverse the diarrhea, abdominal pain, transaminase elevation, AND there are no other causes (such as infection) identified, we will consider the cause of the adverse events to possibly be related to GVHD. In such circumstances, we will make every effort possible to perform biopsies of the involved organ systems to confirm the diagnosis of GvHD.

Dose adjustment for platelet counts and hemoglobin are as the following:

Thrombocytosis	
PLT $\geq 200 \times 10^9 /L$ to $\leq 400 \times 10^9 /L$ at any time	
 • Decrease the dose to the next lower dose level. Wait 2 weeks to assess the effects of this and any subsequent dose adjustments.
PLT $> 400 \times 10^9 /L$ at any time	
 • Stop fostamatinib. Increase the frequency of platelet monitoring to twice weekly. • Once the platelet count is $< 150 \times 10^9 /L$, resume fostamatinib at the next lower dose level

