7.2 PARTICIPANT DISCONTINUATION/WITHDRAWAL FROM THE STUDY

Prior to removal from study, effort must be made to have all subjects complete a safety visit approximately 14 days following the last dose of study therapy.

- Participants are free to withdraw from participation in the study at any time upon request.
- Participants can be taken off study at any time per site principle investigator discretion (e.g. for significant noncompliance or if the PI believes it would be in the subject's best interest).
- Patients rolled over to Extended Access protocol 000760 will be discontinued from this protocol.

The reason for participant discontinuation or withdrawal from the study will be recorded on the Case Report Form (CRF). Subjects who sign the informed consent form but do not receive the study intervention may be replaced.

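### Section 7.1 keeps subjects in follow-up after they stop drug, but three toxicity rules take them off study; week-12 secondary data and late first safety events are lost in those subjects

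*Combined protocol and SAP*

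**What the plan says.** Section 7.1 sets the default: "Discontinuation from the study drug does not mean discontinuation from the study", and the procedures still due are to be carried out. Among the data to be collected when drug is stopped it adds "Patients will be followed for clinical data required for the duration of the study".

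Three other provisions end participation for toxicity:

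- Section 6.1.2.3, intolerance of the lowest dose level: "If unable to tolerate 100mg daily, patient will stop fostamatinib and will be off study".
- Section 6.1.2.3, second febrile neutropenia on the reduced dose: "stop fostamatinib and remove the patient from study".
- Section 7.1, last bullet of the withdrawal list: "If participant has drug interruptions more than 14 days due to toxicity (as defined at 6.1.2.3), participants will be withdrawn from the study". This bullet is mandatory, but the list is introduced as discretionary: "An investigator may discontinue or withdraw a participant from the study for the following reasons".

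For anyone leaving the study, Section 7.2 says that "effort must be made to have all subjects complete a safety visit approximately 14 days following the last dose of study therapy". Sections 8.4.4 and 8.4.5 record adverse events up to the last visit. Section 8.4.3.2, however, requires causality assessment of events to the end of week 16. Section 9.3.4 defines the treatment-related SAE (TRSAE) stopping rule by 12 weeks. Secondary endpoints 2 to 6 in Section 4 all use week-12 information.

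**The concern.** The default and the three toxicity rules cannot both be followed for the same subject, and the plan gives no order of precedence. Sites in this multicenter trial could treat similar subjects differently.

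If the removal rules are followed as written, follow-up ends because of toxicity. Two things are at stake. Week-12 transfusion, corticosteroid, immunosuppressant and cGVHD results would describe mainly subjects who tolerated the drug. The safety rules could also miss a first event that arises after a removed subject's last visit. Section 9.3.4 does not say whether such a subject counts as event-free or as not evaluable for TRSAE by 12 weeks.

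**Working it through.** **1. The primary endpoint.** Inputs from Section 9.1: 11 then 9 subjects; stop if 1 or fewer respond in stage 1; reject if more than 4 of 20 respond; null rate 10%, alternative 35%. The probability of rejection is the sum over x = 2 to 11 of P(X1 = x) × P(X2 ≥ 5 − x), with X1 binomial on 11 and X2 binomial on 9.

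- At 35%: 0.860, which reproduces the stated 86%.
- At 10%: 0.040, within the stated 0.05.

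Sections 9.1 and 9.2.1 count discontinuation for drug-related toxicity as non-response. Following these subjects after they stop drug therefore changes neither the count of responders nor these figures.

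**2. The unobserved window for TRSAE.** If the last dose is at week w and the safety visit takes place two weeks later, the unobserved part of the 12-week window is 12 − (w + 2) = 10 − w weeks.

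| Last dose (week) | Weeks unobserved |
|---|---|
| 2 | 8 |
| 4 | 6 |
| 6 | 4 |
| 8 | 2 |
| 10 | 0 |

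The gap matters only for subjects without a TRSAE so far, since the rule counts each subject once. Such subjects can exist. Intolerance in 6.1.2.3 includes an event of any grade that is distressing enough to stop drug, and the 14-day rule covers neutropenia, LFT elevation and diarrhea, which need not be serious.

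**3. The effect on the TRSAE rule.** Recomputing the boundary from the Beta(1, 3) prior (stop when the posterior probability that the rate exceeds 0.25 is at least 90%) gives the plan's table at every n from 3 to 20. Exact stopping probabilities at true rates 0.1, 0.2, 0.25, 0.3, 0.4 and 0.5 are 0.7%, 8.3%, 18.3%, 32.9%, 66.8% and 90.1%. The plan states 1%, 8%, 19%, 33%, 67% and 90%.

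Now assume that a share f of subjects with a TRSAE have it only after their last visit and are counted as event-free. The observed rate becomes p(1 − f); for example, 0.40 × 0.90 = 0.36. The documents give no value for f.

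| True rate | f = 0 | f = 5% | f = 10% | f = 20% |
|---|---|---|---|---|
| 0.30 | 32.9% | 28.1% | 23.7% | 16.0% |
| 0.40 | 66.8% | 60.3% | 53.5% | 39.6% |

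**4. Week-12 secondary data.** Assume that k of 20 subjects are removed before week 12. The missing share is k/20: 1/20 = 5% to 5/20 = 25%. Section 9.3 has no missing-data rule for these endpoints. To illustrate with secondary endpoint 5 (steroid dose at least halved), assume 6 observed successes:

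- k = 1: completer rate 6/19 = 31.6%; possible range over all 20, 6/20 to 7/20 = 30% to 35%.
- k = 5: completer rate 6/15 = 40%; possible range, 6/20 to 11/20 = 30% to 55%.

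**The case against.** The strongest defence is that 7.1 opens by referring to 6.1.2.3, so the removal rules can be read as specific exceptions to a general default. That reading is possible, but the text does not state it. The 14-day rule also sits in 7.1 itself, as a mandatory bullet under a discretionary heading.

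Several further objections stand and limit the point. A reader might infer any of the following, and the documents support none of them:

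- **That all the worst toxicity leads to loss of follow-up.** AST/ALT at 3 × ULN or higher with direct bilirubin above 2 × ULN, and persistent severe hypertension after a crisis, lead only to drug discontinuation. Those subjects stay under the 7.1 default unless the investigator withdraws them.
- **That safety follow-up simply ends.** The triggering event is recorded, grade 3-4 events and SAEs already known are followed to resolution or stability (8.4.4, 8.4.6), and a safety visit is attempted.
- **That the safety rules lose person-time.** The TRSAE rule counts subjects once each. A subject whose removing event was a TRSAE is already counted, and a later first event would have to be judged drug-related after drug had stopped.
- **That graft-failure monitoring to week 12 is lost.** That rule has no 12-week window, and its main definition uses myeloid chimerism, whereas the schedule lists only B-cell chimerism. Removal mainly costs the fallback based on neutrophil counts.
- **That removal is the main cause of missing cGVHD data.** The schedule has no cGVHD row for anyone, and Section 8.2.1 requires no routine examination after Day 1.

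The documents' only related rates come from prior use of the drug (2.3.1): febrile neutropenia 1%, severe diarrhea 1%, neutropenia 6%, AST/ALT above 3 × ULN 9%. These do not give a removal rate, because the populations differ and not every such event leads to removal.

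**Conclusion.** The point holds in a limited form. The contradiction is explicit and unresolved, and it touches secondary and late safety data only. The primary endpoint, power and type 1 error are unaffected.

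The loss in removed subjects is twofold: week-12 secondary values, and a first TRSAE or graft failure arising after the safety visit in someone not already counted. Its size rests on a removal rate that the documents do not give. The 5% to 25% of missing week-12 values assumes 1 to 5 removals among 20, and the fall in stopping probability assumes the shares f shown above. What does not depend on those assumptions is the direction: under the removal rules the missing data come from subjects with toxicity, and the plan does not say how to treat them. The change is worth making before more data accrue, but the trial's main conclusion does not depend on it.

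**What to change.** Reconcile Sections 6.1.2.3, 7.1 and 7.2 by separating off study drug from off study for the purpose of data collection. A subject whose drug is stopped for toxicity would keep the already scheduled labs and the adverse-event, transfusion, steroid, immunosuppressant and cGVHD data collection to the end-of-study visit. The exceptions would be withdrawal of consent, or an investigator's judgement that continuing is not in the subject's interest. Align the adverse-event capture period in 8.4.4 and 8.4.5 with this.

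In Section 9.3.4, state how a subject not followed to week 12 without a TRSAE counts: event-free, not evaluable, or partly observed. In Section 9.3.3, state how missing week-12 values are handled, and report the number removed for toxicity beside each secondary result.

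None of this alters when drug is held, reduced or stopped, and neither sample size nor power changes. The cost is a text amendment and a few remaining visits for a few subjects. Most can be remote with local labs, although note c of the schedule requires the week-12 visit in person.

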7.2 PARTICIPANT DISCONTINUATION/WITHDRAWAL FROM THE STUDY

Prior to removal from study, effort must be made to have all subjects complete a safety visit approximately 14 days following the last dose of study therapy.

- Participants are free to withdraw from participation in the study at any time upon request.
- Participants can be taken off study at any time per site principle investigator discretion (e.g. for significant noncompliance or if the PI believes it would be in the subject's best interest).
- Patients rolled over to Extended Access protocol 000760 will be discontinued from this protocol.

The reason for participant discontinuation or withdrawal from the study will be recorded on the Case Report Form (CRF). Subjects who sign the informed consent form but do not receive the study intervention may be replaced.

7.3 LOST TO FOLLOW-UP

A participant will be considered lost to follow-up if he or she fails to return for a scheduled visit and is unable to be contacted by the study site staff.

The following actions must be taken if a participant fails to return to the clinic for a required study visit:

- The site will attempt to contact the participant and reschedule the missed visit within one week and counsel the participant on the importance of maintaining the assigned visit schedule and ascertain if the participant wishes to and/or should continue in the study.
- Before a participant is deemed lost to follow-up, the investigator or designee will make every effort to regain contact with the participant (where possible, 3 telephone calls and, if necessary, a certified letter to the participant's last known mailing address or local equivalent methods). These contact attempts should be documented in the participant's medical record or study file.
- Should the participant continue to be unreachable, he or she will be considered to have withdrawn from the study with a primary reason of lost to follow-up.

8 STUDY ASSESSMENTS AND PROCEDURES

8.1 SCREENING PROCEDURES

8.1.1 Screening activities performed prior to obtaining informed consent

Minimal risk activities that may be performed before the subject has signed a consent include the following:

- Email, written, in person or telephone communications with prospective subjects.
- Review of existing medical records to include H&P, laboratory studies, etc.
- Review of existing MRI, x-ray, or CT images.
- Review of existing photographs or videos.
- Review of existing pathology specimens/reports from a specimen obtained for diagnostic purposes.

8.1.2 Screening activities performed after a consent for screening has been signed

The following activities will be performed only after the subject has signed the consent for this study.

- Physical examination
- Pregnancy test (for female subjects of childbearing age)
- Clinical labs (CBC, liver enzymes panel, basic metabolic panel, lactate dehydrogenase, , HIV testing, absolute reticulocyte count, haptoglobin, stool occult blood, urinalysis), if not available

The overall eligibility of the subject to receive the study drug will be assessed once all screening values are available and completion of an eligibility checklist.

8.2 EFFICACY ASSESSMENTS

For all baseline assessments and follow-up visits, refer to the Schedule of Assessments (SOA) for procedure to be done, and details below for each assessment.

The subject's clinical status will be captured on each study biweekly follow up visit through the end of the study.

8.2.1 Clinical Evaluations

Physical examination A targeted physical examination will be performed at baseline prior to initial study product administration on Day 1. The baseline physical examination can be one that is conducted from screening to Day 1. Post-baseline physical examinations will be done only when needed to evaluate possible adverse event(s) (i.e. any new signs or symptoms). WHO bleeding assessment should be done on each follow up visit. No routine physical exam is needed for study visits after Day 1.

Abbreviated Title: Fostamatinib for post-transplant cytopenias

Version Date: 11/28/2023

Radiographic or other imaging assessments.

N/A

8.2.2 Biospecimen Evaluations

Research bloods will be sent to the NIH for processing in either the clinical laboratory or in a NHLBI research lab.

The amount of blood that may be drawn from adult patients (i.e., those persons 18 years of age or older) for research purposes shall not exceed 300 mL over any eight-week period.

Please refer to laboratory manual for further information about processing and shipment.

Table of samples to be collected*				
Test/assay	Volume blood (approx.)	Type of tube	Frequency	Location of specimen analysis
Routine* 
 • CBC • Absolute reticulocyte count • BMP • Hepatic pane • Lactate dehydrogenase • haptoglobin 	3 mL 4 mL	EDTA tube Lithium Heparin tube (light green)	Baseline (prior to treatment) and then biweekly on follow up visits	NIH clinical lab or Clinical Lab At participating sites
Research* 
 • STR Chimerism, CD19 	6 ml	EDTA tube	Baseline, then W4,8,12	NHLBI Research Lab ([name]), NIH Clinical Lab (Molecular Hematology, 2C324)
Research* 
 • Type and screen 	6 mL	EDTA tube	Baseline, then W4, 8, 12	NIH Clinical Lab or, Clinical Lab At participating sites**

Abbreviated Title: Fostamatinib for post-transplant cytopenias

Version Date: 11/28/2023

Table of samples to be collected*				
Test/assay	Volume blood (approx.)	Type of tube	Frequency	Location of specimen analysis
Research* • Immunoglobulins, quantitative (IgA, IgG, IgM)	3.5 mL	Lithium Heparin tube (light green)	Baseline, then W4, 8, 12	NIH Clinical Lab Or, Clinical Lab At participating sites***
Research* • HLA antibodies (Class 1 A, B, C and Class 2 DRB1, DQB1) • MFI	10 mL	EDTA tube	Baseline, then W4, 8, 12	NIH Clinical Lab
Research* • CRP	4 mL	Lithium Heparin tube (light green)	Baseline, then W4, 8, 12	NIH Clinical Lab or Clinical Lab At participating sites
Research* • Erythropoietin	3.5 mL	Red top tube (SST3.5)	Baseline, then W4, 8, 12	NIH Clinical Lab
Research* • IL-6	6 mL	EDTA (lavender)	Baseline, then W4, 8, 12	NHLBI Research Lab ([name])
Research* • Expanded cytokine panel • Thrombopoietin	16 mL	Red top tube (serum)	Baseline, then W4, 8, 12	NHLBI Research Lab ([name])
Research* • Lymphocyte subsets • PBMC	20 mL	Sodium Heparin (green top)	Baseline, then W4, 8, 12	NHLBI Research Lab ([name])

* Residual bloods from clinical care can be transferred to the NHLBI research lab for storage

Abbreviated Title: Fostamatinib for post-transplant cytopenias

Version Date: 11/28/2023

In addition to the research blood requested above, we will request residual blood from clinical labs for research purposes, as available for research purposes.

** If baseline testing is negative, this test can be performed at participating sites. If baseline testing is positive, send it to NIH clinical lab for quantification

*** If clinical lab at participating sites cannot process the listed tests, samples can be sent to NIH clinical lab

